Day 7	SARS-CoV-2 RT-qPCR viral load	7	6	8
Day 10	SARS-CoV-2 RT-qPCR viral load	10	9	11
Discharge*	SARS-CoV-2 RT-qPCR viral load	Day of discharge		

* If the participant is discharged prior to Day 10, the SARS-CoV-2 samples/swabs will be collected on the day of discharge. Thereafter, these samples can be collected by assigned study staff at the participant's home or as an outpatient on the assigned days noted above.

Table 3-4.	Analysis Windows	for Serology for SAR	S-CoV-2 (IgG, IgM, and IgA)
	•		

Visit ID	Testing	Nominal Day	Lower Limit	Upper Limit
Baseline/Day 1#	Serology for SARS-CoV-2 (IgG, IgM, and IgA)	1		1 (pre-dose)
Day 5	Serology for SARS-CoV-2 (IgG, IgM, and IgA)	5	4	6
Day 10	Serology for SARS-CoV-2 (IgG, IgM, and IgA)	10	9	11
Discharge*	Serology for SARS-CoV-2 (IgG, IgM, and IgA)	Day of discharge		
Day 30	Serology for SARS-CoV-2 (IgG, IgM, and IgA)	30	25	35

Includes the serum for SARS-CoV-2 IgG, IgM, and IgA serology collected at Screening.

* If the participant is discharged prior to Day 10, the serology for SARS-CoV-2 will be collected on the day of discharge. Thereafter, these samples can be collected by assigned study staff at the participant's home or as an outpatient on the assigned days noted above.

Clinical scoring using the PEWS (0 to 3 on each of 3 categories) will be recorded at Screening and daily through the duration of dosing. Results will be summarized for each Study Day without windows.

The 7-point Ordinal Scale is an assessment of the clinical status of a given Study day. Each day, the worst (ie, lowest ordinal) score from the previous day will be recorded (ie, on Day 3, the

lowest ordinal score from Day 2 is obtained and recorded for Day 2). Results will be summarized for each Study Day without windows.

3.8.3. Selection of Data in the Event of Multiple Records in an Analysis Visit Window

Depending on the statistical analysis method, single values may be required for each Study Day or analysis window. For example, change from baseline by visit usually requires a single value, whereas a time-to-event analysis does not require 1 value per Study Day or analysis window.

If multiple valid, nonmissing measurements exist for a Study Day/analysis window, records will be chosen based on the following rules if a single value is needed:

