6.2. Secondary Efficacy Endpoints

6.2.1. Definition of Secondary Efficacy Endpoints

Clinical improvement based on scoring using the 7-point Ordinal Scale

Clinical improvement improvement based on scoring using the 7-point Ordinal Scale will be derived as follows:

- If a participant dies while hospitalized (as recorded on the Death Report eCRF and Hospitalization Information eCRF), the endpoint on the day of death and all subsequent days through Day 10 will be set to Death (=1).
- If the participant is discharged alive, the endpoint on the day of discharge alive and all subsequent days through Day 10 will be set to Not hospitalized (=7).
- If the participant is discharged alive and dies on the same day or a later day (as recorded on the Death Report eCRF and Hospitalization Information eCRF), the endpoint on the day of discharge alive and all subsequent days until the day of death will be set to Not hospitalized (=7). On the day of death and all subsequent days through Day 10, the endpoint will be set to Death (=1).

Every effort will be made to obtain clinical status data for all participants prior to discharge alive. The last known clinical status will be used for days with missing clinical status (eg, where the reason for Hospital Discharge is not "Discharged Alive" and the participant has not died). All postbaseline days with missing ordinal scale score, from Day 2 to Day 10, will use the previous last known clinical status.

Clinical improvement is investigated in two settings:

- ≥ 1 point improvement from baseline clinical status or discharged alive
- \geq 2-point improvement from baseline clinical status or discharged alive on the 7-point ordinal scale

Recovery is defined as an improvement from a baseline score of 2 through 5 to a score of 6 or 7, or an improvement from a baseline score of 6 to a score of 7.

Clinical improvement based on scoring using the PEWS Improvement Scale

Clinical improvement is investigated in two settings:

- ≥ 1 point improvement from baseline clinical status or discharged alive
- \geq 2-point improvement from baseline clinical status or discharged alive on the 7-point ordinal scale

Recovery is defined as an improvement from a baseline score of 1-3 to a score of 0, or being discharged alive, whichever comes first.

Time (days) to discharge from hospital

- Duration of hospitalization from Day 1 = number of days from first dose to date discharged alive.

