- Total duration of hospitalization = number of days from hospital admission to date discharged alive.

Oxygen usage and ventilation modality and settings

Oxygen support status is defined based on the 7-point ordinal scale.

Days to the first confirmed negative PCR result

• Confirmed negative PCR result is defined as 2 consecutive negative PCR results or a negative PCR result at the last available sample for participants who completed or discontinued from this study.

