cumulative incidence from the competing risk analysis for each PEWS improvement scale category (behavior, cardiovascular, respiratory) will also be graphically presented. Furthermore, the number and percentage of participants with $a \ge 1$ -point improvement or discharged alive on Day 2 through Day 10 or discharged alive for each PEWS improvement scale category (behavior, cardiovascular, respiratory) will be summarized by cohort and overall total.

Time to recovery based on the PEWS scale on Day 2 through Day 10, and last available assessment will be modelled using a competing risk analysis for each PEWS improvement scale category (behavior, cardiovascular, respiratory). The competing event is death. Participants not achieving a score of 0 at the last assessment will be censored on the day of the last clinical assessment. In addition, the cumulative incidence from the competing risk analysis for each PEWS improvement scale category (behavior, cardiovascular, respiratory) will also be graphically presented. Furthermore, the number and percentage of paricipants with recovery based on the PEWS scale on Day 2 through Day 10, and last available assessment for each PEWS improvement scale category (behavior, cardiovascular, respiratory) will be summarized by cohort and overall total.

Time (days) to discharge from hospital

Time to discharge from hospital will be modelled using a competing risk analysis. The competing event is death. Participants not discharged from hospital will be censored on the day of the last clinical assessment. In addition, the cumulative incidence from the competing risk analysis will also be graphically presented.

Descriptive statistics for duration of hospitalization from Day 1 and total duration of hospitalization will also be provided for each cohort and overall total. In addition, information on hospitalization status will be summarized for each cohort and overall total. Only participants who are discharged alive on or prior to Day 30 will be included in the duration of hospitalization through Day 30 follow-up visit analysis.

Oxygen usage and ventilation modality and settings

Descriptive statistics will be provided by cohort and overall total for the number of days of oxygen support through discharge alive, death or Day 10 based on the 7-point ordinal scale reported values, including:

- Days on invasive mechanical ventilation
- Days on high flow oxygen devices
- Days requiring low flow supplemental oxygen

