- Time to ≥ 2 point improvement and time to ≥ 1 point improvement: if a participant did not experience the event of interest and did not die, the participant was censored at the last non-missing assessment date. Participants who died were considered to have experienced a competing event.
- Time to recovery: Participants not achieving recovery at the last assessment were censored on the day of the last assessment. Participants who died were considered to have experienced a competing event.
- Time to discharge from hospital: Participants not discharge at the last assessment were censored on the day of the last clinical assessment. Participants who died were considered to have experienced a competing event.

18) Details on the LOQ and LOD for the viral load samples are provided below.

Table 13-3.Viral Load Sample Details

Sample type	Limit of quantitation (copies/mL)	Limit of detection (copies/mL)
Nasal/oropharyngeal samples Nasopharyngeal/oropharyngeal samples ET aspirates	1018	925
Rectal or fecal swabs	488	306

- 19) Quantitative and categorical summary on SARS-CoV2 results and change from baseline in SARS-CoV-2 viral load up to Day 10 or up to the first confirmed negative PCR result (whichever comes first)
 - For quantitative summary (e.g., mean viral load, change from baseline etc.), "Inconclusive" SARS-CoV2 result is set to missing
 - For categorical SARS-CoV2 summary, 3 categories will be included, i.e. Positive, Inconclusive, Negative
 - Positive = Any numeric result or "< 1018cp/mL SARS-CoV-2 detected" (for Nasal/oropharyngeal samples, Nasopharyngeal/oropharyngeal samples, or ET aspirates) or "< 488cp/mL SARS-CoV-2 detected" (for rectal or fecal swabs)
 - Negative = "No SARS-CoV2 detected"
 - Inconclusive = "Inconclusive"

20) Days to the first confirmed negative PCR result

- Categorical SARS-CoV2 and SARS-CoV2 negative summary will be separated out by sample type. There will be no combined positive or negative category using 2 or 3 sample types.
- Confirmed negative PCR result is defined as 2 consecutive negative results, or negative at last available sample for participants who completed or discontinued from study. Notice 2 negative results from the same day do not equal confirmation.
- For a negative SARS-CoV2 confirmation, "Inconclusive" SARS-CoV2 result will not be considered as missing thus a "Negative" followed by a "Inconclusive" is NOT a confirmed negative PCR result.

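### Does limiting the hospital-stay table to live discharges by Day 30, with a loosely named censoring day for time to discharge, call for a change?

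*SAP*

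**What the plan says.** Section 6.2.1 defines two durations, both ending at live discharge: "Duration of hospitalization from Day 1 = number of days from first dose to date discharged alive" and "Total duration of hospitalization = number of days from hospital admission to date discharged alive". Section 6.2.2 adds the inclusion rule for the table: "Only participants who are discharged alive on or prior to Day 30 will be included in the duration of hospitalization through Day 30" follow-up visit.

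The same part of Section 6.2.2 plans a competing-risk analysis of time to discharge, with death as the competing event and a plotted cumulative incidence, and a summary of hospitalization status by cohort and overall. The Full Analysis Set is the primary set. Its censoring rule is "Participants not discharged from hospital will be censored on the day of the last clinical assessment". Appendix 3 item 17 repeats it: "Participants not discharge at the last assessment were censored on the day of the last clinical assessment".

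Item 17 words its rules for the other endpoints differently. For improvement, "the participant was censored at the last non-missing assessment date"; for recovery, "Participants not achieving recovery at the last assessment were censored on the day of the last assessment".

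**The concern.** Two things look wrong.

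- **The table is conditional on its own outcome.** A child still in hospital at Day 30 has a longer stay from Day 1 than any child in the table, yet is left out. The SAP does not say that a median or quartiles will be read off the cumulative incidence curve, so the only durations promised as numbers come from the selected group. In a cohort of 12, one long stay could matter.
- **The censoring day is not pinned down.** Section 3.8.2 says "The 7-point Ordinal Scale is an assessment of the clinical status of a given Study day", and Section 1.2 stops that scoring with dosing, so by Day 10. Appendix 1 also schedules examination, vital signs and respiratory status at the Day 30 (± 5 days) visit. The last clinical assessment could therefore be either. If a programmer took discharge dates through Day 30 but censored at the last ordinal score, the censoring would be informative and the curve too high.

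**Working it through.** The SAP gives no figure for stay, discharge or death, so there is none to reproduce. Everything numerical below rests on assumed counts. Let N be the number of children, k the number still in hospital at Day 30, and m the mean stay from Day 1 among those discharged (assumed 7 to 10 days). N = 52 is the minimum total in Section 1.3, and 12 is the size of each of Cohorts 1-4.

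**1. The table, stay from Day 1.** A child in hospital at Day 30 has stayed at least 30 − 1 = 29 days from first dose. Ignoring deaths, including k such children raises the mean by at least

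((N − k)·m + 29k)/N − m = (k/N)·(29 − m).

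| N | k | m = 10 | m = 7 |
|---|---|---|---|
| any | 0 | 0 | 0 |
| 52 | 1 | 19/52 = 0.37 d | 22/52 = 0.42 d |
| 52 | 5 | 95/52 = 1.83 d | 110/52 = 2.12 d |
| 12 | 1 | 19/12 = 1.58 d | 22/12 = 1.83 d |

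I also compared quartiles, discharged children only against the curve, under lognormal stays truncated at 29 days (median/log-SD 6/0.8, 8/0.8, 8/1.0, 10/0.8), N = 52, no deaths. With k = 1 neither the median nor the upper quartile moves. With k = 5 the median moves 0 to 1 day and the upper quartile 2 to 3 days.

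**2. Direction.** The downward shift holds only for stay from Day 1 and only for children still in hospital. Total stay runs from admission, so a discharged child with a long stay before first dose can exceed one still in hospital at Day 30. If days in hospital were counted for children who died, leaving out an early death would lengthen the mean, not shorten it.

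**3. The censoring day.** Three readings, N = 52:

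- *Day 30 visit.* Children not discharged remain at risk throughout. With no deaths the curve ends at (52 − k)/52: 51/52 = 98.1% for k = 1, 47/52 = 90.4% for k = 5. No bias.
- *Events and censoring both stopped at Day 10.* No bias, but a short curve. Under the lognormal stays above, without deaths, it ends at 44% to 71% for k from 0 to 5, and the upper quartile is not reached.
- *Censoring at Day 10, later discharges still counted.* With no deaths, everyone left at risk after Day 10 is eventually discharged, so the curve ends at 100%. The excess is 100 − 98.1 = 1.9 points for k = 1 and 100 − 90.4 = 9.6 points for k = 5. With two assumed deaths (12 and 20 days after first dose), it ends at 95% to 96% instead of 94.2% (k = 1) to 86.5% (k = 5).

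**4. Which reading the document supports.** The discharge paragraph itself works through the Day 30 follow-up visit, and Appendix 1 schedules clinical assessments there. Section 6.2.1 takes discharge and death from the Hospitalization Information and Death Report forms, not from the ordinal score. For the PCR endpoint, Section 6.2.2 uses the same phrase and Appendix 3 item 20 makes it the last day with a PCR result. The phrase is thus shorthand for the last assessment relevant to the endpoint; for discharge, that is the last record of hospital status. The other wordings in item 17 belong to other endpoints and do not contradict it.

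**The case for a change.** The strongest case for a change is the censoring day. In the ordinal-scale and PEWS paragraphs of Section 6.2.2 the same phrase most naturally means the last score. PCR received its own date in Appendix 3 and discharge did not. Section 3.8.1 defines a Last Study Date that can include the follow-up visit, but the discharge rule does not refer to it. The mixed reading always biases upward, and naming the date would cost one sentence. If many children stayed, the error would be large: with an assumed 26 discharged by Day 10, 10 later, 3 deaths and 13 still in hospital, discharge by Day 30 reads 90.1% instead of 69.2%.

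What stands is that the term is undefined for discharge. The rest does not carry far. The large gap needs both the least likely reading and a quarter of the children still in hospital, a count nothing in the SAP supports.

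On the table, extra quartiles, a label and three counts would be pleasant to have, but much of this is already there. The rule states the condition, Section 3 reports n for continuous variables, hospitalization status is summarized, and Section 7.1.6.1 summarizes and lists deaths.

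**Conclusion.** No change is needed. The table describes what it says it describes, children discharged alive by Day 30, and stands beside an analysis that keeps everyone else. More output would correct no error. The censoring day is a small gap in wording that an analyst would fill sensibly with the last record of hospital status, through the Day 30 visit; that reading and the consistent Day 10 reading are both unbiased.

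If no child is still in hospital at Day 30, the table is unaffected on this account. With one such child, its mean stay from Day 1 is short by at least about 0.4 days in 52, or 1.6 to 1.8 days in a cohort of 12. No direction can be claimed for total stay or for excluded deaths. These sizes rest on assumed counts and an assumed mean of 7 to 10 days. The endpoint is secondary and descriptive, with no formal test, so no study conclusion turns on it.

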Participants will be treated for up to 10 days. Those participants who have demonstrated clinical improvement may be considered for a shorter treatment period.

Screening is to be completed within 2 days prior to the Day 1 visit.

At the screening visit and all subsequent study visits (or until hospital discharge - whichever comes first) laboratory analyses (hematology, chemistry, inflammatory markers, urinalysis, and routine coagulation test), vital signs (heart rate, temperature, blood pressure [mean arterial pressure if available, systolic and diastolic], respiratory rate [if not on a ventilator], oxygen saturation), complete or symptom-directed physical examinations will be performed. Nasopharyngeal and oropharyngeal samples (combined) OR nasal and oropharyngeal samples (combined), and rectal or fecal swab will be collected on Days 1, 3, 5, 7, and 10 (if feasible) for SARS-CoV-2 reverse transcriptase quantitative polymerase chain reaction (RT-qPCR) viral load testing and possible viral resistance testing. Endotracheal tube aspirates will also be collected if the participant is intubated. If the participant is discharged prior to Day 10, the samples for SARS-CoV-2 RTqPCR viral load testing and possible viral resistance testing and possible viral resistance testing can be collected by assigned study staff at the participant's home or as an outpatient on the assigned days noted above, if feasible. Serum for SARS-CoV-2 IgG, IgM, and IgA serology will be collected at Screening, Day 5, Day 10 (if feasible), and the Day 30 Follow-up visit (for participants weighing ≥ 12 kg).

Clinical scoring using PEWS and the Ordinal Scale will occur at Screening and daily through the duration of dosing.

Adverse events and concomitant medications will be assessed from Screening through the Day 30 Follow-up visit.

As many of the specified sparse PK assessments should be obtained from each participant as is feasible.

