3.1.2. Full Analysis Set

The Full Analysis Set (FAS) includes all enrolled participants who received at least 1 dose of study drug. This is the primary analysis set for efficacy analyses.

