6.2.2. Analysis of Secondary Endpoints

The FAS will be the primary analysis set for secondary efficacy endpoints. No formal statistical testing is planned.

Clinical improvement based on scoring using the 7-point Ordinal Scale

For each cohort and overall total, clinical status and change from Baseline in clinical status by Study Day as well as last available assessment will be summarized by the number and percentage of participants for each category. It should be noted that the main timepoint of interest for this endpoint is Day 10. In addition, a stacked bar chart will also be provided for each cohort and overall total depicting the percentage of participants for each category by Study Day. Furthermore, descriptive statistics for change from Baseline in clinical status by Study Day and last available assessment will also be provided for each cohort and overall total. Time to clinical improvement (days) will be modelled using a competing risk analysis. The competing event is death. Participants not achieving clinical improvement at the last assessment will be censored on the day of the last clinical assessment. In addition, the cumulative incidence from the competing risk analysis will also be graphically presented. The number and percentage of participants with clinical improvement will also be summarized by cohort and overall total.

Time to \geq 1-point improvement from baseline clinical status or discharged alive on the 7-point ordinal scale will be modelled using a competing risk analysis. The competing event is death. Participants not achieving \geq 1-point improvement at the last assessment will be censored on the day of the last clinical assessment. In addition, the cumulative incidence from the competing risk analysis will also be graphically presented. Furthermore, the number and percentage of participants with a \geq 1-point improvement or discharged alive based on the 7-point ordinal scale on Day 2 through Day 10 as well as last available assessment will be summarized by cohort and overall total.

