As oxygen support status will be collected only while the participant is in the hospital, if a participant is discharged alive and dies afterwards, the participant will be included only in the summary for participants discharged alive.

Change from baseline in SARS-CoV-2 viral load up to Day 10 or up to the first confirmed negative PCR result (whichever comes first)

Descriptive statistics for viral load and change from baseline in viral load will be provided by cohort and overall total for the following:

- Day of discharge and each study day up to Day 10 or up to the first confirmed negative PCR result (whichever comes first)
- Day of discharge and each study day up to Day 10

Separate summary tables will be provided for each sample type: (a) nasal/oropharyngeal samples, (b) nasopharyngeal/oropharyngeal samples, (c) endotracheal tube (ET) aspirates, and (d) rectal or fecal swabs.

Days to the first confirmed negative PCR result, where confirmed is defined by 2 consecutive negative PCR results

For each cohort and overall total, the number and percentage of participants with:

- At least 1 negative PCR result
- Confirmed negative PCR result

will be summarized separately for each sample type: (a) nasal/oropharyngeal samples, (b) nasopharyngeal/oropharyngeal samples, (c) ET aspirates, and (d) rectal or fecal swabs.

Time to first confirmed negative PCR result will be modelled separately for each sample type: (a) nasal/oropharyngeal samples, (b) nasopharyngeal/oropharyngeal samples, (c) ET aspirates, and (d) rectal or fecal swabs, using a competing risk analysis. The competing event is death. Participants not not achieving a confirmed negative PCR at the last assessment will be censored on the day of the last clinical assessment.

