7.2.2.2. Summaries of Laboratory Abnormalities

Laboratory data that are categorical will be summarized using the number and percentage of participants in the study with the given response at baseline and each scheduled postbaseline time point.

The following summaries (number and percentage of participants) for treatment-emergent laboratory abnormalities will be provided by lab test and treatment group; participants will be categorized according to the most severe postbaseline abnormality grade for a given lab test:

- laboratory abnormalities
- Grade 3 or 4 laboratory abnormalities

For all summaries of laboratory abnormalities, the denominator is the number of participants with nonmissing postbaseline values up to 30 days after last dosing date.

A by-participant listing of laboratory abnormalities will be provided by subject ID number and visit in chronological order. This listing will include all test results that were collected throughout the study for the lab test of interest, with all applicable severity grades displayed.

Abnormalities in coagulation parameters will be graded for INR, PT, and aPTT.

For the INR of prothrombin time and aPTT, protocol specified toxicity grading scale depends on the upper limit of normal range (ULN). While the ULN of INR and aPTT depends on whether the participant is taking anticoagulant medication or not (ie, Not taking oral anticoagulant: 0.8 - 1.2; Taking oral anticoagulant: 2.0 - 3.0), this information is not collected by the reference laboratory. As a result, INR and aPTT will be graded by assuming participant is not taking an oral anticoagulant, which is a conservative approach that may lead to over-reporting of abnormalities for INR and aPTT.

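### The by-specimen PCR-negative endpoint has no denominator other than the FAS, and its two censoring rules conflict, so children never sampled in a specimen can dilute its clearance figures

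*SAP*

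**What the plan says.** Section 6.2.2 states that "The FAS will be the primary analysis set for secondary efficacy endpoints". Section 3.1.2 defines that set: "The Full Analysis Set (FAS) includes all enrolled participants who received at least 1 dose of study drug". No sample is required.

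For days to the first confirmed negative PCR, Section 6.2.2 then asks for "For each cohort and overall total, the number and percentage of participants with" at least one negative and with a confirmed negative result. This is done separately for nasal/oropharyngeal samples, nasopharyngeal/oropharyngeal samples, endotracheal (ET) aspirates, and rectal or fecal swabs. No denominator is given. Appendix 3 item 20 adds: "There will be no combined positive or negative category using 2 or 3 sample types".

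Section 1.2, repeated in Section 3.8.2, says who can have each specimen: "Nasopharyngeal and oropharyngeal samples (combined) OR nasal and oropharyngeal samples (combined), and rectal or fecal swab will be collected", and "Endotracheal tube aspirates will also be collected if the participant is intubated".

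The time-to-event analysis has two censoring rules. Section 6.2.2 says that participants not "achieving a confirmed negative PCR at the last assessment will be censored on the day of the last clinical assessment". Appendix 3 item 20 instead censors them on the last day on which a PCR result is available, without saying that the result must be of the sample type being analysed.

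Section 3.7 leaves out of the viral load analysis participants negative at baseline, viral loads of participants given IV remdesivir before enrollment, and samples taken once other COVID-19 treatment has begun. It does not say whether these exclusions cover the PCR-negative endpoint, and none of them concerns a child with no sample of a given type.

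**The concern.** Missing specimens are built into this design. A child swabbed by one upper-airway method need not have the other, and a child who is never intubated has no ET aspirate. Such a child cannot be observed to turn negative in that specimen. If the child still counts in the denominator or the risk set, the result mixes how often a specimen was taken with how often it cleared. Specimens and cohorts then cannot be compared, because swab choice and intubation can differ between them. No pooled result is available to compensate.

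The SAP does set observed-data denominators elsewhere. For laboratory abnormalities (Section 7.2.2.2), "the denominator is the number of participants with nonmissing postbaseline values up to 30 days after last dosing date". Liver tests (Section 7.2.3) and PK time points (Section 8.2.1) have similar rules. This endpoint, where availability varies by design, has none.

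In a single-arm study without formal testing, these percentages and curves are read as absolute values, so their denominators determine what they mean.

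**Working it through.** The SAP gives no clearance rate, no share of children sampled and no PCR denominator, so there is no figure of its own to reproduce. The inputs below are assumptions, except N = 52, the minimum sample size in Section 1.3.

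**Percentages.** With k children clearing, m sampled and N in the FAS, the FAS percentage is k/N = (m/N) × (k/m), that is, the share sampled times clearance among those sampled. Taking about half of sampled children as clearing:

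| Sampled (m) | Clearing (k) | FAS denominator | Sampled-only denominator |
|---|---|---|---|
| 5 | 2 | 2/52 = 3.8% | 2/5 = 40.0% |
| 13 | 6 | 6/52 = 11.5% | 6/13 = 46.2% |
| 26 | 13 | 13/52 = 25.0% | 13/26 = 50.0% |
| 39 | 20 | 20/52 = 38.5% | 20/39 = 51.3% |

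If all are sampled, the two agree.

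A further consequence for the two upper-airway types: if each child has only one swab method, their FAS percentages cannot sum to more than 100%. Even if every child cleared, at least one would read 50% or less.

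**Curves.** Assume no deaths, so that cumulative incidence equals 1 minus Kaplan-Meier. Take 26 of 52 sampled and 13 clearing: 4 on Day 3 and 3 on each of Days 5, 7 and 10. The other 13 sampled children are censored at Day 10. The 26 unsampled children are then handled in turn as follows:

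- Not in the risk set, or censored at Day 0: 1 − (22/26)(19/22)(16/19)(13/16) = 1 − 13/26 = 50.0%.
- Section 6.2.2 rule, last clinical assessment on Day 10 or later: 1 − (48/52)(45/48)(42/45)(39/42) = 1 − 39/52 = 25.0%.
- Section 6.2.2 rule, last clinical assessment on Day 5: 1 − (48/52)(45/48)(16/19)(13/16) = 1 − 0.592 = 40.8%.

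With 13 of 52 sampled and 6 clearing (2 each on Days 3 and 5, 1 each on Days 7 and 10), the same three cases give 46.2%, 11.5% and 28.2%.

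**The Appendix 3 rule.** If it means the last result of the same sample type, a never-sampled child has no censoring date and adds nothing, so the curve stays at 50.0%. If it means any PCR result, a child never intubated but swabbed to Day 10 stays in the ET-aspirate risk set to Day 10, and the 25.0% case returns. The wording does not decide between the two.

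**The case against.** A reader might infer that the SAP sets these percentages on the whole FAS and counts never-sampled children as not cleared. The text does not go that far. Section 6.2.2 names the FAS as the primary set for secondary efficacy endpoints in general and gives no denominator for these percentages. No section classes an unsampled child as a failure, and Section 3.6.1 says that missing data are generally not imputed. In the curves such children would be censored, which is not the same as failing.

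A reader might also infer that the curves are diluted in any case. They are not if Appendix 3 item 20 governs and is read per sample type. Even under Section 6.2.2, the size depends on when the last clinical assessment falls. Nor does the argument from alternative or conditional specimens reach all four types, since rectal or fecal swabs are planned for every child.

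Finally, the viral load tables are split by the same sample types and report n, so a reader would have some sight of how many children were sampled.

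These points limit the size and certainty of the effect, but the gap remains. Not imputing a value does not remove a child from a denominator, and the FAS is the only set named. The viral load tables would not let a reader rebuild a diluted curve. The two censoring rules still conflict, and neither defines the risk set.

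**Conclusion.** The point stands as a denominator left to the FAS by default, together with two conflicting censoring rules. Followed literally, the SAP scales by-specimen clearance down by the share of children sampled. The curves are scaled by up to the same factor under the Section 6.2.2 rule, and not at all under a type-specific reading of Appendix 3. In the illustration with half the children sampled, 50.0% becomes 25.0% for the percentage, and between 25.0% and 40.8% on the curve for a last clinical assessment between Day 10 and Day 5. The effect would be largest for a specimen that few children have, which may be ET aspirates.

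The direction follows from arithmetic. The sizes rest on assumed shares, clearance rates and clearance days. The endpoint is secondary and descriptive, so severity is modest, but the SAP should be corrected because its stated rules can produce a misleading figure.

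**What to change.** Amend Section 6.2.2 and Appendix 3 item 20 together:

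1. For each sample type, include only FAS participants with at least one PCR result of that type who are not negative at baseline in that type. Show this n as the denominator.
2. Do not require a postbaseline result for the competing-risk analysis, so that children who die before one is taken still count under the competing event. Do not require a baseline result of that type either, since that would drop children intubated after Day 1 from the ET analysis.
3. Replace the Section 6.2.2 censoring rule with a single rule used in both places: the last available PCR result of that sample type.
4. State that the Section 3.7 exclusions apply to this endpoint.

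The cost is a few sentences and a small programming change. Section 1 already provides for documenting changes made after SAP finalization in the study report. The downside is smaller, openly shown denominators, possibly very small for ET aspirates.
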